 - Serum ferritin <30ug
 - o Hgb <10 g/dl
- Between 24 34 weeks gestation
- Plan to deliver at an in-network hospital
- Able and willing to give informed consent

Exclusion criteria

- Diagnosis of non-iron-deficiency anemia
- Multiple gestation
- Known or suspected major fetal anomalies or aneuploidy
- Planned delivery at out-of-network hospital
- Unable or unwilling to give consent

Randomization and treatment: Patients who meet all inclusion criteria and no exclusion criteria will be enrolled and randomized in a 1:1 ratio using a computer-generated randomization sequence to one of two treatment protocols:

- 1. Oral Iron Supplement- Oral iron supplementation (ferrous sulfate 325mg once daily to three times daily through delivery)
- 2. Intravenous Iron- Intravenous iron infusion (1000mg of intravenous iron dextran; given as a single dose after enrollment as close as possible to 24 weeks gestation). If iron dextran is unavailable due to drug shortage, ferumoxytol will be substituted; 510 mg IV will be administered followed by a second dose (510 mg IV) 3 to 8 days after the initial dose.

Procedures: All patients presenting for prenatal care will have workup for anemia with repeat CBC at 24 to 28 weeks gestation per standard of care. Patients found to have iron-deficiency anemia (Hgb <10 g/dL and ferritin <30ug) at 24 – 28 weeks and who meet all other inclusion and exclusion parameters will be eligible to be approached for the study. In addition, patients who do not receive standard anemia screening but are diagnosed at 28 – 34 weeks gestation with iron-deficiency anemia (hemoglobin<10mg/dl and ferritin <30ug) will be eligible for the study. Subjects will be randomized to one of the two treatment groups (oral or intravenous iron supplementation). Study patients will have Hgb and ferritin drawn at delivery. Their neonates will have Hgb and ferritin drawn via cord blood at delivery. If a cord gas or umbilical artery lactate level is drawn out of clinical necessity, this data will be collected also. Chart abstraction will be used to assess additional maternal and neonatal outcomes. Pregnancy, labor and delivery management will be per standard obstetric practice.

Sample Size: 120 subjects over an estimated 15 - 18 months.

BACKGROUND

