Overview: We will conduct an open-label, randomized controlled trial to assess the effectiveness and safety of treating iron-deficiency anemia in pregnant women with intravenous iron compared with oral iron. We test the *hypothesis* that treating iron-deficiency anemia with intravenous iron is associated with improved maternal and neonatal outcomes compared with oral iron. We will use broad inclusion criteria and analyze data using the intention-to-treat principle to increase generalizability of the findings.

Inclusion & exclusion criteria:

Inclusion criteria:

- Pregnant women
- 18 years or older
- Diagnosed with iron-deficiency anemia
 - Serum ferritin <30ug
 - o Hgb <10 g/dl
- Between 24 34 weeks gestation
- Plan to deliver at an in-network hospital
- Able and willing to give informed consent

Exclusion criteria:

- Diagnosis of non-iron-deficiency anemia
- Multiple gestation
- Known or suspected major fetal anomaly or aneuploidy
- Planned delivery at out-of-network hospital
- Unable or unwilling to give consent

Study outcomes:

Primary outcome: The primary outcome of the trial is maternal anemia, defined as Hgb <11mg/dl, on admission for labor and delivery.

Secondary outcomes:

- 1. Safety:
 - i. Mild/moderate infusion reactions: chest tightness, itching, urticaria, flushing, nausea/vomiting, arthralgia, back or joint aches, mild shortness of breath, tachycardia, hypertension or hypotension, abdominal pain, diarrhea, peripheral edema, headache, dizziness, syncope, or numbness.
 - ii. Major infusion reaction: anaphylaxis-like reaction, seizures, or non-reassuring fetal heart rate tracing.

2. Maternal outcomes:

- i. Hgb at admission to labor and delivery
- ii. Hgb on postpartum day 1
- iii. Ferritin at admission to labor and delivery
- iv. blood transfusion
- v. mode of delivery
- vi. postpartum disposition
- vii. readmission

3. Neonatal outcomes

- i. gestational age at delivery
- ii. birth weight
- iii. cord gases (if performed as SOC)
- iv. umbilical artery lactate (if performed as SOC)
- v. APGAR scores
- vi. Hgb (obtained from cord blood)
- vii. Ferritin (obtained from cord blood)
- viii. neonatal morbidities
- ix. postpartum disposition

Screening:

[figure not shown]

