Pregnant women attending prenatal care will be screened for anemia with repeat CBC at 24 to 28 weeks gestation per standard of care. If the initial Hgb at this gestational age is less than 10 mg/dL, they will undergo testing for iron-deficiency anemia. Iron-deficiency anemia will be defined as anemia with serum ferritin <30ug. Any pregnant woman diagnosed with iron-deficiency anemia who meets all inclusion criteria and no exclusion criteria will be eligible for the study (**Figure 1**). In addition, patients who present for prenatal care after 28 weeks gestation who meet all inclusion criteria and no exclusion criteria will be eligible for enrollment if they are diagnosed with iron-deficiency anemia prior to 34 weeks.

Randomization and Treatment Groups: Patients meeting all inclusion criteria and no exclusion criteria who sign informed consent will be enrolled and randomly assigned in a 1:1 ratio using a computer-generated randomization sequence to one of two treatment protocols. The two treatment protocols are:

- 1. Oral Iron Supplement- Oral iron supplementation will occur throughout pregnancy with ferrous sulfate at a dose range of 325mg daily to 325mg three times daily. Patients will be instructed to take on an empty stomach or with an acidic beverage like orange juice. Patients will continue oral iron supplementation through delivery, then refer to their treating physician for further postpartum consumption. Patients will be asked to report any side effects of oral iron between 2 4 weeks after randomization. Side effects will also be assessed at delivery along with reported compliance to the oral iron regimen.
- 2. Intravenous Iron- The intravenous iron infusion will occur in the form of 975mg of intravenous iron dextran diluted in 250 or 500mL of 0.9% sodium chloride given as a single dose over 1-2 hours. Prior to starting the treatment dose, participants will receive a test dose of 0.5mL (25mg) of iron dextran and will be monitored by hospital nursing staff for 20-30 minutes (or per local infusion protocol) to ensure there are no transfusion IVIDA.Version [6.2] 09.18.2019

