Maternal blood draw: Serum ferritin	SOC			х	
Cord blood collection & processing (Hgb & ferritin; cord gas and/or lactate if performed as clinical necessity)				Х	
Delivery & neonatal outcomes via chart abstraction					Х

^{*}If ferumoxytol is administered due to shortage of iron dextran, two infusions will occur in the prenatal period as outlined in the randomization section of this document. The post-infusion phone call will occur 48-72 hours after the second infusion.

Data analysis: Analyses will follow the intention to treat principle, in which patients will be analyzed in the group to which they were randomized whether or not they received the assigned treatment. Continuous variables will be compared using the Student's t-test or Mann Whitney t test, as appropriate. Categorical variables will be compared using the t or Fisher's exact test, as appropriate. We will calculate crude and unadjusted risk estimates and differences. We will use multivariable logistic regression to adjust for potential confounders. We will estimate the number needed to treat to prevent occurrence of one primary outcome.

Sample size estimation: Based on institutional data the baseline rate of anemia (Hgb<11mg/dl) on admission to labor and delivery among women on supplemental oral iron is 38.5%. We estimate that 108 patients will provide 80% power to detect a 60% or greater relative difference in anemia (38.5% versus ≤15.4%) with intravenous iron (alpha=0.05, 2-tailed test). We will recruit **120 patients** to account for an anticipated 10% loss to follow-up (**Table 1**).

The anticipated effect size of 60% is plausible and conservative. A study by Al *et al.*, the only study that reported the outcome of Hgb <11 at the time of delivery, showed an effect size of 88% (4.4% versus 37.8%, RR 0.12, 95% CI 0.03, 0.48).⁴ Based on preliminary data showing that 10 pregnant women received intravenous iron in 6 weeks at the Washington University Medical Center, we anticipate that the 124 patients will be recruited within 15 months.

Table 1: Sample size estimation (Baseline: 38.5%, Power: 80%, alpha 0.05, loss: 10%)				
Risk Estimate RR (%)	Anticipated Rate	N	N+10%	
0.67 (33)	25.8%	418	460	
0.60 (40)	23.1%	276	304	
0.50 (50)	19.3%	168	185	
0.40 (60)	15.4%	108	120	
0.33 (67)	12.7%	82	90	
0.30 (70)	11.6%	74	81	

HUMAN SUBJECTS PROTECTION

Assessment of Risks

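### Delivery hemoglobin and ferritin are compared without the screening values that every participant has, at a modest cost in precision

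*Combined protocol and SAP*

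**What the plan says.** The analysis plan is the Data analysis paragraph under Study Procedures in the combined protocol and SAP.

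- **Continuous outcomes:** "Continuous variables will be compared using the Student's t-test or Mann Whitney t test, as appropriate". No baseline term or change score is mentioned.
- **Binary outcomes:** "We will calculate crude and unadjusted risk estimates and differences. We will use multivariable logistic regression to adjust for potential confounders". No covariate is named.
- **Number needed to treat (NNT):** "We will estimate the number needed to treat to prevent occurrence of one primary outcome".

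The secondary maternal outcomes include "Hgb at admission to labor and delivery" and "Ferritin at admission to labor and delivery".

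Both quantities are also measured at entry. The Synopsis (Procedures) makes eligible "Patients found to have iron-deficiency anemia (Hgb <10 g/dL and ferritin <30ug", the inclusion criteria repeat both cut-offs, and Figure 2 lists both blood draws at screening as standard of care. Screening is described as "Pregnant women attending prenatal care will be screened for anemia with repeat CBC at 24 to 28 weeks gestation per standard of care". Later presenters "will be eligible for enrollment if they are diagnosed with iron-deficiency anemia prior to 34 weeks".

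**The concern.** A pre-randomization measurement of the same quantity is usually the natural covariate for a continuous outcome. Here it exists for every eligible participant, needs no extra blood draw, and is left out of the comparison. The logistic model does not fill the gap, because it cannot be applied to delivery Hgb or ferritin as continuous measures.

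At stake is the width of the confidence intervals for two laboratory outcomes that describe directly how well each treatment corrects the deficiency. With only 108 evaluable patients planned, precision that costs nothing is worth having.

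**Working it through.** **1. The plan's own figure.** The Sample size estimation paragraph gives 38.5% v 15.4%, two-sided alpha 0.05, 80% power and 108 evaluable patients. The unpooled two-proportion formula is

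n per arm = (z₀.₉₇₅ + z₀.₈₀)² × [p₁(1−p₁) + p₂(1−p₂)] / (p₁−p₂)²
= 7.849 × (0.2368 + 0.1303) / 0.231² = 53.99,

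so 54 per arm and 108 in total, as stated. It is an unadjusted calculation, and nothing below alters it.

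**2. What correlation is plausible.** The documents give none, so r is an assumption. Enrolling only women with low values narrows the baseline range and weakens r. If screening and delivery values are bivariate normal with full-range correlation ρ, and v is the variance of the truncated baseline relative to the full range, then

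r = ρ√v / √(ρ²v + 1 − ρ²).

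For the lowest 5%, 10% and 20%, v = 0.138, 0.169 and 0.219.

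| Full-range ρ | r among enrolled (lowest 5% to 20%) |
|---|---|
| 0.3 | 0.12 to 0.15 |
| 0.5 | 0.21 to 0.26 |
| 0.6 | 0.27 to 0.33 |
| 0.7 | 0.34 to 0.42 |

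I take r = 0.2 to 0.3 as the working range. The share of women below the cut-offs is also an assumption. Entry spans 24 to 34 weeks, so the interval from screening to delivery varies, which adds to the uncertainty in r.

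**3. Gain from ANCOVA, 54 per arm.** The variance factor is 1 − r². The equivalent number of extra patients is 108 × [1/(1 − r²) − 1]. Estimating one slope costs a factor of about 106/105, giving the net column.

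| r | Variance factor | Extra patients | Net of slope |
|---|---|---|---|
| 0 | 1.00 | 0 | −1.0 |
| 0.2 | 0.96 | 4.5 | 3.4 |
| 0.3 | 0.91 | 10.7 | 9.6 |
| 0.5 | 0.75 | 36.0 | 34.6 |

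A simulation (20,000 trials, screening Hgb drawn from the lowest 10% of a normal distribution) agrees. At r = 0, 0.2 and 0.3 the ratio of ANCOVA to t-test variance was 1.010, 0.968 and 0.912. The ratio of interval widths was 1.005, 0.984 and 0.959. ANCOVA type I error was 4.7%, 4.9% and 5.2%.

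**4. Power (noncentral t).**

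- *Illustrative 0.5 SD difference in Hgb:* t-test 73.1%. ANCOVA gives 74.8% at r = 0.2 and 77.0% at r = 0.3, or 74.4% and 76.6% net of the slope.
- *Shift implied by the design rates:* if delivery Hgb is normal with equal SD in both arms, 38.5% and 15.4% below 11 correspond to z = −0.292 and −1.019, a shift of 0.727 SD. The t-test then has 96.3% power, and ANCOVA 96.7% (r = 0.2) or 97.4% (r = 0.3) net of the slope.

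**5. Validity of the planned test.** In a separate simulation with a true difference of 0.54 SD, the t-test and ANCOVA both averaged 0.54. The t-test's type I error was 4.8 to 5.2%.

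**6. Scale for ferritin.** Screening ferritin is cut at 30, so its shape says little about delivery ferritin. For lognormal ferritin (assumed median 12 to 30, log-SD 0.5 to 0.9), skewness is −0.3 to 0.7 below 30 but 1.8 to 4.8 without the cut. A rule that chose the scale from screening values could keep the raw scale for a strongly skewed outcome.

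**The case against.** The case for leaving the plan alone is reasonable. The t-test and Mann-Whitney are valid under randomization, these are secondary outcomes, the correlation is a guess, and for ferritin there is not even an indirect basis for one. If the treatment effect is as large as the design assumes, power for Hgb is already 96% and the only gain is a slightly narrower interval. All of this stands. It limits the size of the point, but it does not make omitting the baseline value a better choice.

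A reader might be tempted to go further in three ways.

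- *That the plan has no route to a risk difference or NNT.* This is true only of the logistic model, whose coefficient is an odds ratio. The same paragraph plans crude risk differences, and 1/0.231 gives an NNT of 4.3 at the design rates. The sample size calculation is also unadjusted, so the crude comparison is the implied primary one. The pairing of two synonyms in the risk-estimate sentence looks like a slip, though the text does not settle it.
- *That leaving the covariates unnamed inflates the trial's type I error.* Simulated rates of about 7 to 10% arise only if someone searches every subset of five candidate covariates for the smallest p-value and uses the result as the trial's test. The plan calls for no such search, and the crude test is unaffected.
- *That adjustment would materially raise power for the primary outcome.* At r = 0.2 the variance of the risk difference hardly changes (ratio 0.99 to 1.00). Neither power nor type I error for the primary outcome is a reason for this change.

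**Conclusion.** The point holds as a modest loss of precision on delivery Hgb and delivery ferritin. It is not a bias, and it leaves the primary comparison intact. At an assumed r of 0.2 to 0.3 the variance is about 4 to 9% larger than it need be, equivalent to roughly 3 to 10 patients on 108. At r = 0 nothing is lost.

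The word modest depends on that range. At r = 0.5 among enrolled women the variance reduction would be 25%, but under the truncation model even a full-range correlation of 0.7 gives only 0.34 to 0.42. For ferritin the same factors apply at the same r, with less basis for choosing it.

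The unnamed covariates, the paired synonyms and the unstated source of the NNT are clarifications of what the plan already implies. The change is worth making because it is free, not because the trial fails without it.

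**What to change.** In the Data analysis paragraph, add text to this effect:

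> Delivery Hgb will be compared by ANCOVA with screening Hgb as covariate. Delivery ferritin will be compared by ANCOVA of log delivery ferritin on log screening ferritin; the log scale is fixed in advance. Mann-Whitney will be a sensitivity analysis for ferritin. Other continuous outcomes will be compared by t-test or Mann-Whitney.

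As a minor clarification of the binary analyses:

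> For the primary outcome the crude comparison is primary and gives the NNT. Any adjusted logistic analysis of it is secondary, with screening Hgb (and gestational age at randomization, if wanted) as the named covariates.

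Correct the paired synonyms in the risk-estimate sentence so that it states whether adjusted estimates are intended.

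The cost is small: no new data, no more patients, and no change to the 108 evaluable or 120 recruited. Each ANCOVA uses one degree of freedom, which widens the interval by about 0.5% if the correlation is zero. The ferritin effect would be reported as a ratio of geometric means, not as a difference in means.

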- v. The study team will monitor, document and report to the Institutional Review Board, any adverse events among study participants per the plan detailed below.

Reportable Events

The PI at each site will oversee the safety of the study at his/her site. During the study, the investigator or study site personnel will be responsible for querying and recording adverse events (AEs) and serious adverse events (SAEs), as detailed below.

Types of Reportable Events:

Serious Adverse Events (SAE)

The site must report all SAEs to the lead site, whether or not they result from study participation, within 24 hours of learning of the event. A serious adverse event (SAE) is any adverse event occurring within the timelines specified in the protocol that results in any of the following outcomes:

- Death
- Life-threatening situation (subject is at immediate risk of death)
- Inpatient hospitalization or prolongation of existing hospitalization
- Persistent or significant disability/incapacity
- Congenital anomaly/birth defect in the offspring of a subject who received study drug
- Important medical events that may not result in death, be immediately life-threatening, or require hospitalization, may be considered an SAE when, based upon appropriate medical judgment, they may jeopardize the subject and may require medical or surgical intervention to prevent one of the outcomes listed in this definition.

Adverse Events (AE)

An adverse event is any untoward medical occurrence in a clinical investigation subject administered an investigational product and which does not necessarily have to have a causal relationship with this treatment. An AE can, therefore, be any unfavorable and unintended sign (that could include a clinically significant abnormal laboratory finding), symptom, or disease temporally associated with the use of a medicinal product, whether or not considered related to the medicinal product.

For this study, abnormal laboratory findings (e.g., clinical chemistry, hematology) or other abnormal assessments (e.g., electrocardiogram, X-rays, vital signs) per se are not reported as AEs. Only the Adverse Events of Special Interest (AESI) defined below will be recorded on the CRFs and in the subject's chart.

Adverse Events of Special Interest (AESI)

Adverse events of particular clinical importance (other than SAEs mentioned above) will be classified as adverse events of special interest (AESIs). For this study, AESIs refer to:

• Mild/moderate reactions:

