- Other major deficiencies in informed consent or HIPAA authorization process or documentation (e.g., substantive outdated informed consent or HIPAA content, such as missing study procedures information, that may affect subjects' willingness to participate).

Study Conduct Events Reportable at IRB Renewal:

Events that do not meet the criteria for prompt reporting should be reported at the time of next study renewal to ensure the IRB has a full understanding of the conduct of the research. **Events that must be reported with the next study renewal submission include:**

- Protocol deviations/protocol noncompliance not previously reported to the IRB.
- Minor noncompliance (i.e., likely not serious or continuing), such as:
 - Use of a consent form that is not the most recently-approved version when the content is not substantively different from the current IRB approved consent.
 - Use of an unstamped consent form when the content is the same as the current IRB approved version.
 - Enrolling more subjects than approved by the IU IRB.
 - Conduct of research by individuals not listed on the study protocol but who have completed appropriate investigator requirements.
 - o Implementing minor wording changes to IRB study documents without prior IRB approval.
 - Failure to appropriately document consent and/or authorization, if the missing information can be clearly corroborated by other documentation (e.g., research notes).

Data Monitoring and Quality Control

Periodic monitoring visits will be made at the investigational site throughout the clinical study to ensure that the investigator obligations are fulfilled, and all applicable regulations and guidelines are being followed. These visits will ensure that the facilities remain acceptable, the investigational plan is being followed, the IRB and local authorities have been notified of approved investigational plan changes as required, complete records are being maintained, appropriate and timely reports have been made to the sponsor and/or its designees and the IRB, and the investigator is carrying out all agreed upon activities.

An annual report will be generated beginning one year after the first enrollment and will include the following:

- A list and summary of adverse events;
- Whether adverse event rates are consistent with pre-study assumptions;
- A summary of recruitment and retention and reason for dropouts;
- Whether the study is on track to be completed and accomplish the stated aims.

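### Does the forecast of 124 patients in 15 months put the recruitment target of 120 in doubt?

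*Combined protocol and SAP*

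**What the plan says.** The synopsis, under Sample Size, plans for "120 subjects over an estimated 15 - 18 months". The Sample size estimation paragraph derives 108 evaluable patients for 80% power to detect 38.5% versus 15.4% anemia at a two-sided 5% level. It raises this to 120 "to account for an anticipated 10% loss to follow-up", and the 60% reduction row of Table 1 repeats 108 and 120.

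The next paragraph turns to feasibility. It cites preliminary data that "10 pregnant women received intravenous iron in 6 weeks at the Washington University Medical Center" and concludes that "we anticipate that the 124 patients will be recruited within 15 months". The number 124 appears nowhere else in the protocol.

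Two other places bear on the point. Under Reportable Events, "The PI at each site will oversee the safety of the study at his/her site", so more than one site is foreseen. Under Data Monitoring and Quality Control, "An annual report will be generated beginning one year after the first enrollment", and one of its items is "Whether the study is on track to be completed and accomplish the stated aims".

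**The concern.** A reader meets two totals, 120 and 124, within two paragraphs, and the wording of the second refers back to a total that was never set. The sentence also presents its timeline as a consequence of the cited rate, yet that rate does not give 124, or even 120, in 15 months. The synopsis gives a longer window.

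If 124 were a live target, it would be unclear how many women the trial means to randomize and what loss allowance applies. If the timeline mattered, the annual report would have no single yardstick for judging whether recruitment is on track.

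**Working it through.** **Is 120 the right operative figure?** The inputs from the Sample size estimation section are p1 = 0.385, p2 = 0.154, two-sided alpha 0.05, power 80% and loss 10%; allocation is 1:1. With the unpooled normal approximation, the number per arm is

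(1.960 + 0.842)² × [p1(1 − p1) + p2(1 − p2)] / (p1 − p2)²
= 7.849 × (0.2368 + 0.1303) / 0.0534
= 53.99, rounded up to 54.

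That makes 108 in total, the plan's own number. The same formula reproduces every N in Table 1. Allowing for 10% loss, 108 / 0.9 = 120.0; multiplying instead, 108 × 1.1 = 118.8. Neither gives 124. So 120 is derived and 124 is not.

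**Does the forecast follow from the cited rate?** Take 365.25 / 12 / 7 = 4.348 weeks per month.

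| Quantity | Calculation | Result |
|---|---|---|
| Recruits in 15 months | 65.2 weeks × 10/6 | 108.7 |
| Recruits in 18 months | 78.3 weeks × 10/6 | 130.4 |
| Time to 120 | 72.0 weeks / 4.348 | 16.6 months |
| Time to 124 | 74.4 weeks / 4.348 | 17.1 months |

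Counting 4 or 4.5 weeks to a month gives 100 or 112.5 recruits in 15 months, so month length does not explain the gap. With calendar months, the times to 120 and to 124 both fall inside the synopsis window of 15 to 18 months.

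**How firm is 108.7?** It rests on 10 events. The exact Poisson 95% interval is 4.80 to 18.39 per 6 weeks. Multiplied by 65.22 / 6, that is about 52 to 200 recruits in 15 months. If the rate were known to be exactly 10 per 6 weeks, the chance of reaching 120 by 15 months would be 15%. Allowing for uncertainty in the rate (assumption: a gamma distribution for the rate with shape 10 to 11, giving a gamma-Poisson prediction), the chance is about 35% to 46%.

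**Does 124 distort the annual report?** Assume even accrual. At 12 months the benchmarks are:

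- 124 in 15 months: 124 × 12/15 = 99.2
- 120 in 15 months: 120 × 12/15 = 96.0
- 120 in 18 months: 120 × 12/18 = 80.0

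Of the 19.2-patient spread between the highest and lowest, the numeral accounts for 99.2 − 96.0 = 3.2. The other 16.0 is the width of the synopsis range and would remain if 124 were corrected.

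**The case for a change.** The strongest case for acting is that the error can be verified on the page, the correction is one numeral, and the sentence claims to derive a timeline that its own rate does not deliver. The annual report must comment on progress, and the cited rate projects to 52.2 weeks × 10/6 = 87.0 at 12 months: behind 124 in 15 months, ahead of 120 in 18.

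What stands is that 124 is wrong and that 15 months is not a straight projection of the cited rate. The rest carries little weight:

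- The durations overlap, so they differ in wording and do not contradict each other.
- The rate counts women given intravenous iron at one center, not women eligible for or consenting to randomization. The Background says that the US recommendation reserves intravenous iron for women who cannot or will not take oral iron, so recipients may be only part of the eligible population. Refusal of consent would pull the other way. The protocol refers to several sites but gives no per-site rate or consent fraction.
- The annual report sets no numeric benchmark, and most of the spread comes from the synopsis's deliberate range.

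**Conclusion.** This is a clerical slip with no consequence for the trial. The recruitment target is 120, stated consistently in the synopsis, the sample size paragraph and Table 1, and reproduced from the plan's inputs. The stray figure exceeds it by 4 patients (4/120 = 3.3%) and feeds no calculation, decision rule or analysis. An analyst or trial manager reading the section would work to 120 without hesitation.

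The 15-month forecast is optimistic against a simple projection (108.7 recruits; 16.6 months to reach 120), but it sits at the edge of the stated window, and the evidence behind the rate is too thin to refute it. This rests on calendar months, constant accrual and, for the interval, Poisson counts. The numeral can be tidied whenever the document is next revised, but the point does not justify a revision of its own. Sample size, power, procedures and conclusions would be the same either way.
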